6 CRITERIA FOR SUBJECT ENROLLMENT

6.1 Target Disease (Diagnosis Group)

Patients with hypercalcemia in parathyroid carcinoma or PHPT who are unable to undergo PTx or relapse after PTx

6.2 Inclusion Criteria

Subjects enrolled in this study should satisfy all of the following criteria.

- 1) Personally submitted written voluntary informed consent to participate in the study
- 2) Aged \geq 20 years at the time of consent
- 3) A diagnosis of parathyroid carcinoma or PHPT who are unable to undergo PTx or relapse after PTx
- 4) Corrected serum Ca level > 11.3 mg/dL at screening

6.3 Exclusion Criteria

Any individuals falling under any of the following criteria should not be enrolled in this study.

- 1) Treatment with cinacalcet hydrochloride (e.g., Regpara[®]) within 2 weeks before screening
- 2) Start of treatment with denosumab (e.g., Ranmark[®] and Pralia[®]), bisphosphonates* and calcitonins for the treatment of hypercalcemia, and zoledronic acid hydrate (e.g., Reclast[®]) for the treatment of osteoporosis; change in dose or dosing regimen of such drugs; or change in type of such drugs within 12 weeks before screening
*: Alendronate sodium hydrate (e.g., Teiroc[®]), zoledronic acid hydrate (e.g., Zometa[®] and zoledronic acid), and pamidronate disodium hydrate (e.g., Aredia[®])
- 3) Start of treatment with an active vitamin D preparation or its derivative, Ca preparation, bisphosphonates* for the treatment of osteoporosis, or calcitonins for purposes other than the treatment of hypercalcemia; change in dose or dosing regimen of such drugs; or change in type of such drugs within 2 weeks before screening
*: Alendronate sodium hydrate (e.g., Fosamax[®]), ibandronate sodium hydrate (e.g., Bonviva[®]), etidronate disodium (e.g., Didronel[®]), minodronic acid hydrate (e.g., Recalbon[®]), and sodium risedronate hydrate (e.g., Benet[®])
- 4) Current or history of serious drug allergy. Drug dependence or alcohol dependence and/or their past history
- 5) Severe heart disease (e.g., Class \geq III per New York Heart Association classification; see Attachment 5 of the protocol [supplementary volume])
- 6) Severe hepatic impairment (e.g., treatment with antiviral therapy)
- 7) Uncontrolled hypertension or diabetes
- 8) History of diagnosis and treatment of malignant tumor within 5 years before screening (excluding parathyroid carcinoma, basal cell carcinoma, or surgically resected intraepithelial carcinoma of uterine cervix)
- 9) Treatment with another investigational product (drug or unapproved medical device) in a clinical study or any study equivalent to clinical study within 12 weeks before screening

- 10) Pregnant, lactating, possibly pregnant female subject (subjects who have been amenorrheic for at least 12 months after the last menstrual period without an alternative medical cause are to be considered to have no childbearing potential) with positive pregnancy test at screening or with negative pregnancy test at screening who is unwilling to use adequate contraception according to the physician's instructions or wishes to become pregnant during participation in the study
- 11) Diagnosis of hypercalcemia induced by malignant tumor other than parathyroid carcinoma
- 12) History of participating in a study of KHK7580 and prior exposure to KHK7580
- 13) Other subjects unfit for participation in this study in the judgment of the investigator or subinvestigator

7 REGIMEN AND CONCOMITANT THERAPY

7.1 Dose, Mode of Administration, and Dosing Period

7.1.1 Dose and Mode of Administration

7.1.1.1 Dosage and Administration (Dose per Administration and Dosing Frequency)

Study treatment will start with once-daily administration of KHK7580 2 mg (daily dose: 2 mg).

However, the starting dose may be KHK7580 2 mg twice daily (daily dose: 4 mg) for subjects with a corrected serum Ca level of > 12.5 mg/dL at screening. Thereafter, the dosage will be adjusted in accordance with Section 7.1.1.2 "Dose Adjustment Criteria" until completion or discontinuation of the study. KHK7580 will be administered orally every day at any dosage and administration specified in (1) to (6), and administration at any other dosage and administration will not be allowed.

- (1) 2 mg once daily (daily dose: 2 mg)
- (2) 2 mg twice daily (daily dose: 4 mg)
- (3) 4 mg twice daily (daily dose: 8 mg)
- (4) 6 mg twice daily (daily dose: 12 mg)
- (5) 6 mg three time daily (daily dose: 18 mg)
- (6) 6 mg four times daily (daily dose: 24 mg)

7.1.1.2 Dose Adjustment Criteria

7.1.1.2.1 Criteria for Dose Increase

In principle, dose increase will be performed on the day of scheduled visit. If all of the following criteria are met, the dose will be increased on a step-by-step basis in accordance with the dose and mode of administration specified in (1) to (6), Section 7.1.1.1.

- Corrected serum Ca level > 10.3 mg/dL at the time of hospital visit.
- The current dose has been administered for at least 2 weeks.
- There are no safety problems with dose increase in the subject in the judgment of the investigator or subinvestigator.

7.1.1.2.2 Dose Reduction

The dose will be reduced if the investigator or subinvestigator determines that the dose should be reduced due to the occurrence of an adverse event, etc. In principle, the dose of the study drug will be reduced on a step-by-step basis; however, if the investigator or subinvestigator deems it necessary, the dose may be reduced by two or more levels at a time. In that case, the lowest possible dose is 2 mg once daily (daily dose: 2 mg). If it is judged that the dose should be reduced further while once-daily administration at a dose of 2 mg is performed (daily dose: 2 mg), study treatment will be interrupted.

7.1.1.2.3 Dose Increase After Dose Reduction

In principle, the first dose increase after dose reduction will be performed on the day of scheduled visit. Dose increase may be performed when the investigator or subinvestigator determines that the dose can be increased. In principle, dose increase will be performed on a step-by-step basis; however, if the investigator or subinvestigator deems it necessary, the dose may be increased by two or more levels at a time, provided that the post-increase dose matches the dosage and administration immediately before dose reduction.

7.1.1.2.4 Criteria for Treatment Interruption

Study drug administration will be interrupted if any of the following criteria is met.

- Corrected serum Ca level ≤ 7.5 mg/dL.
- The investigator or subinvestigator has determined that study drug administration should be interrupted due to the occurrence of an adverse event, etc.
- The investigator or subinvestigator has determined that the dose should be reduced while the study drug is administered at a dose of 2 mg once daily (daily dose: 2 mg).

7.1.1.2.5 Resumption of Study Drug Administration After Interruption

In principle, study drug administration will be resumed on the day of scheduled visit. Administration will be resumed after the corrected serum Ca level has reached or exceeded 8.4 mg/dL AND the investigator or subinvestigator has judged that administration can be resumed in consideration of the safety of the subject. The dosage and administration at the time of resumption of administration will be the same as those immediately before interruption or the dosage and administration at a lower level.

The duration of an interruption should not exceed 8 consecutive weeks; if the investigator or subinvestigator has judged that it is impossible to resume administration, the subject will be withdrawn from the study.

7.1.2 Dosing Period (Study Length)

52 weeks (the evaluation period [up to 24 weeks] and the extended administration period combined)

7.2 Concomitant Drugs and Therapies (Concomitant Medications)

If a drug or therapy other than the study drug was used between Week 0 and the completion or discontinuation of the study, the following information will be entered into the eCRF. However, concomitant therapy will be entered only if it is used as a treatment for the underlying disease.

- Name of drug/therapy (reported name of drug, med, or therapy)
- Route of administration
- Duration of treatment (start date of medication / end date of medication)
- Reason for use (indication)

With regard to the restricted concomitant medications (Section 7.2.2), however, information about “dosing frequency per interval” and “total daily dose,” in addition to the items listed above, will be entered into the eCRF for the following drugs: active vitamin D preparations and their derivatives, Ca preparations, calcitonins not intended for the treatment of hypercalcemia, and bisphosphonates for the treatment of osteoporosis used from 2 weeks before screening until the completion or discontinuation of

the study; zoledronic acid hydrate (e.g., Reclast[®]) for the treatment of osteoporosis and denosumab (Pralia[®]) used from 12 weeks before screening until the completion or discontinuation of the study. No entries are necessary for fluid replacement with physiological saline or dissolution media for non-therapeutic purposes, local anesthetics for pain relief at the time of indwelling needle puncture, or contrast media for diagnostic imaging.

7.2.1 Prohibited Concomitant Medication

Cinacalcet hydrochloride (e.g., Regpara[®]) may not be concomitantly used during the study participation period. This drug should not be used from 2 weeks before screening until the completion or discontinuation of the study.

7.2.2 Restricted Concomitant Medications

If the following restricted concomitant medications are used, changes in the type or dosage and administration thereof will be prohibited from 2 weeks before screening until the completion or discontinuation of the study for 1) to 4), and from 12 weeks before screening until the completion or discontinuation of the study for 5) to 8). Also, in subjects who are not using any of these restricted concomitant medications, administration of a restricted concomitant medication may not be newly started during these time frames.

- 1) Active vitamin D preparations and their derivatives
- 2) Ca preparations
- 3) Calcitonins not intended for the treatment of hypercalcemia
- 4) Bisphosphonates for the treatment of osteoporosis (including those not listed below)
 - Alendronate sodium hydrate (e.g., Fosamax[®])
 - Ibandronate sodium hydrate (e.g., Bonviva[®])
 - Etidronate disodium (e.g., Didronel[®])
 - Minodronic acid hydrate (e.g., Recalbon[®])
 - Sodium risedronate hydrate (e.g., Benet[®])
- 5) Zoledronic acid hydrate for the treatment of osteoporosis. (e.g., Reclast[®])
- 6) Denosumab (e.g., Ranmark[®] and Pralia[®])
- 7) Calcitonins for the treatment of hypercalcemia
- 8) Bisphosphonates for the treatment of hypercalcemia (including those not listed below)
 - Alendronate sodium hydrate (e.g., Teiroc[®])
 - Zoledronic acid hydrate (e.g., Zometa[®] and zoledronic acid)
 - Pamidronate disodium hydrate (e.g., Aredia[®])

8 REGISTRATION IN THE STUDY

8.1 Method of Subject Registration

The investigator or subinvestigator will provide a thorough explanation about this study to prospective subjects and obtain written informed consent for participation in the study if they are deemed to satisfy the inclusion criteria and not to fall under any of the exclusion criteria. After obtaining written informed consent, the investigator or subinvestigator will send a fax to the contact address indicated in Section 8.4 by means of the Case Registration Form for the KHK7580 Phase 3 Clinical Study (see Attachment 3 of the protocol [supplementary volume]) for subjects whose eligibility has been confirmed through screening. Registration will be carried out in accordance with the provisions of Section 8.2.

8.1.1 Assignment of Subject Identifiers

The investigator or subinvestigator will assign subject identifiers to all subjects who have given their consent at the study site in accordance with the following rules. The same subject identifier will be used for a subject throughout the study participation period. The last four digits of the subject identifier (XX-YY) will be used as the subject number.

Subject identifier: 7580-101-XX-YY

XX: Site number (see Attachment 1 of the protocol [supplementary volume])

YY: Serial number of the subject who has given his/her consent at the study site

For example, the subject identifier of a subject who was the first to give his/her consent at a study site (site number: 01) would be 7580-101-01-01.

When assigning a subject identifier to a subject, the investigator or subinvestigator will record the subject identifier in the screening log.

8.2 Registration Procedure

Subject registration will be carried out in accordance with the following procedures.

- 1) After obtaining informed consent, the investigator or subinvestigator will perform screening.
- 2) The investigator or subinvestigator will check subjects against all inclusion and exclusion criteria, prepare the Case Registration Form for the KHK7580 Phase 3 Clinical Study (see Attachment 3 of the protocol [supplementary volume]) for all subjects who have given their consent, whether or not the criteria are met, and notify the Study Registration Center described in Section 8.4 by fax. Registration will be done during the period from the date on which checking results for all inclusion and exclusion criteria are obtained (after screening results are known) until the start of study drug administration. However, if a subject withdraws consent or is found to be ineligible after consent has been obtained, the Case Registration Form for the KHK7580 Phase 3 Clinical Study (see Attachment 3 of the protocol [supplementary volume]) should be prepared promptly and faxed to the Study Registration Center described in Section 8.4.
- 3) The 7580-101 Study Registration Center will verify the eligibility of subjects. The 7580-101 Study Registration Center may inquire with the investigator or subinvestigator before the scheduled date of study drug administration if any questions arise about the information provided at the time of registration. For subjects who do not satisfy the inclusion criteria and/or fall under

any of the exclusion criteria, the investigator or subinvestigator will enter the reason for ineligibility, subject identifier, date of obtaining written informed consent, and sex in the eCRF.

4) The investigator or subinvestigator will record and maintain a screening log of registered subjects.

8.3 Re-registration

Subjects who were found to be ineligible may be re-registered at the discretion of the investigator or subinvestigator, provided that consent is obtained anew and the subjects undergo screening once again. When a subject who was once found to be ineligible is re-registered, a new subject identifier will be assigned.

9 OBSERVATION, INVESTIGATION, AND EXAMINATION ITEMS AND SCHEDULE

9.1 Schedule

Screening will be performed in subjects who have given their written informed consent. Afterwards, the study drug will be administered to subjects whose eligibility has been confirmed and for whom registration has been completed, and observation, investigation, and examination will be performed according to the schedule described in Table 9.1-1 and Table 9.1-2. Details are given in Section 9.3 “Observation and Investigation Items and the Timing Thereof” and Section 9.4 “Examination Items and the Timing Thereof.” Visits and examinations will be carried out on the scheduled visit dates with an allowable window of ± 4 days during the period between Week 2 and Week 24, and on the scheduled visit dates with an allowable window of ± 7 days thereafter. If a decision is made to discontinue study drug administration on a day of scheduled visit, the results of the examination on that scheduled visit date may be handled as the results of withdrawal examination.

Table 9.1-1. Observation, investigation, and examination schedule (evaluation period)

	Obtaining informed consent	Screening	Registration	Evaluation period														1 At discontinuation
				Time after administration of the study drug (Weeks)														
				0	2	4 ^e	6 ^e	8 ^f	10 ^f	12 ^g	14 ^g	16 ^h	18 ^h	20 ⁱ	22 ⁱ	24 ^j		
Time after administration (h)				Before administration	0.5	1	2	3										
Obtaining informed consent	X																	
Study drug administration					←												→	
Subject demographics	X ^a																	
Registration		X																
Height	X ^a																	
Body weight				X														X X
QOL assessment				X														X X
Vital sign				X				X X	X X	X X	X X	X X	X X	X X	X X	X X	X X	
Hematology				X				X X	X X	X X	X X	X X	X X	X X	X X	X X	X X	
Blood biochemistry 1	X ^b			X				X X	X X	X X	X X	X X	X X	X X	X X	X X	X X	
Blood biochemistry 2				X				X X	X X	X X	X X	X X	X X	X X	X X	X X	X X	
Urinalysis				X				X X	X X	X X	X X	X X	X X	X X	X X	X X	X X	
Plasma drug concentration ^c				X X X X	X X ^k			X ^k		X ^k		X ^k		X ^k		X ^k		
Pregnancy test ^d	X																	X
Electrocardiogram (12-lead)				X				X X	X X	X X	X X	X X	X X	X X	X X	X X	X X	
Adverse events					←												→	
Confirmation of the use status of concomitant medications	←																	→
Investigation of administration status					←												→	

The allowable window period is ± 4 days of the scheduled visit dates (except for Week 0).

a) Performed after informed consent is obtained and before the start of study drug administration (Week 0).

b) Corrected serum Ca, Ca, and Alb levels will be measured. In the event that the test result does not meet inclusion criteria 4), re-testing may be performed. If performed in Week 0, it will be handled as a test result in Week 0.

c) From Week 2 onwards, if a subject is not taking the study drug as of the day before his/her visit to the hospital, it is permissible not to perform blood collection on the day of hospital visit. It is also permissible not to perform post-dose blood collection in a subject for whom a decision to interrupt study drug administration has been made on the day of hospital visit.

d) Female subjects only. However, no pregnancy test is required if at least 12 months have passed since the last menstrual period without any other medical reason.

e) Subjects whose corrected serum Ca level has been maintained at ≤ 10.3 mg/dL for 2 weeks will immediately transition to the extended administration period, with the next visit being Week 8.

f) Subjects whose corrected serum Ca level has been maintained at ≤ 10.3 mg/dL for 2 weeks will immediately transition to the extended administration period, with the next visit being Week 12.

g) Subjects whose corrected serum Ca level has been maintained at ≤ 10.3 mg/dL for 2 weeks will immediately transition to the extended administration period, with the next visit being Week 16.

h) Subjects whose corrected serum Ca level has been maintained at ≤ 10.3 mg/dL for 2 weeks will immediately transition to the extended administration period, with the next visit being Week 20.

i) Subjects whose corrected serum Ca level has been maintained at ≤ 10.3 mg/dL for 2 weeks will immediately transition to the extended administration period, with the next visit being Week 24.
 j) Subjects whose corrected serum Ca level has been maintained at ≤ 10.3 mg/dL for 2 weeks will immediately transition to the extended administration period, with the next visit being Week 28.
 k) If the subject transitions to the extended administration period, plasma drug concentrations may be measured at the end of the evaluation period (0.5, 1, 2, and 3 hours) (see Table 9.1-2 "Observation, investigation, and examination schedule (extended administration period)").
 l) If a decision is made to discontinue study drug administration on a day of scheduled visit, the results of the examination on that scheduled visit date may be handled as the results of withdrawal examination.

Table 9.1-2. Observation, investigation, and examination schedule (extended administration period)

	Extended administration period													^h At the first visit following dose increase or resumption after interruption	ⁱ At discontinuation		
	Time after the start of study drug administration (Weeks)																
	8 ^a	12 ^b	16 ^c	20 ^d	24 ^e	After the end of the evaluation period ^f				28 ^f	32	36	40	44	48	52	
Time after administration (h)						0.5	1	2	3								
Study drug administration (h)	←										→						X
Body weight					X												X
QOL assessment					X												X
Vital sign	X	X	X	X	X					X	X	X	X	X	X	X	X
Hematology	X	X	X	X	X					X	X	X	X	X	X	X	X
Blood biochemistry 1	X	X	X	X	X					X	X	X	X	X	X	X	X
Blood biochemistry 2	X	X	X	X	X					X	X	X	X	X	X	X	X
Urinalysis	X	X	X	X	X					X	X	X	X	X	X	X	X
Plasma drug concentration ^g	X ⁱ	X ⁱ	X ⁱ	X ⁱ	X ⁱ	X	X	X	X								
Pregnancy test ^k																	X
Electrocardiogram (12-lead)	X	X	X	X	X					X	X	X	X	X	X	X	X
Adverse events	←																→
Confirmation of the use status of concomitant medications	←																→
Investigation of administration status	←																→

The allowable window for the scheduled visit dates is ± 4 days until Week 24 and ± 7 days thereafter.

a) For subjects who completed the evaluation period in Week 4 or 6, hospital visits in the extended administration period will start in Week 8.
 b) For subjects who completed the evaluation period in Week 8 or 10, hospital visits in the extended administration period will start in Week 12.
 c) For subjects who completed the evaluation period in Week 12 or 14, hospital visits in the extended administration period will start in Week 16.
 d) For subjects who completed the evaluation period in Week 16 or 18, hospital visits in the extended administration period will start in Week 20.

- e) For subjects who completed the evaluation period in Week 20 or 22, hospital visits in the extended administration period will start in Week 24.
- f) For subjects who completed the evaluation period in Week 24, hospital visits in the extended administration period will start in Week 28.
- g) If a subject is not receiving the study drug as of the day before his/her visit to the hospital, it is permissible not to perform blood collection on the day of hospital visit. It is also permissible not to perform post-dose blood collection in a subject for whom a decision to interrupt study drug administration has been made on the day of hospital visit.
- h) If the dose of the study drug is increased (with or without prior dose reduction) or administration is resumed after an interruption on a scheduled visit date, the date 2 weeks after the dose increase or resumption will be designated as the date of post-dose-increase (or post-resumption) visit, and scheduled tests will be performed on that date.
- i) If measurement of plasma drug concentrations was not performed after the end of the evaluation period (0.5, 1, 2, and 3 hours), it should be performed by Week 24.
- j) On this date, subjects should not take the study drug before hospital visit.
- k) Female subjects only. However, no pregnancy test is required if at least 12 months have passed since the last menstrual period without any other medical reason.
- l) If a decision is made to discontinue study drug administration on a day of scheduled visit, the results of the examination on that scheduled visit date may be handled as the results of withdrawal examination.

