9.2 Subject Demographics

The following items will be investigated and entered into the eCRF.

- Date of informed consent
- Sex
- Date of birth
- Medical history – Complication
- Medical history – Past medical history
- Medical history – Primary disease
- Date of diagnosis for primary disease
- Occurrence of pharmacotherapy for primary disease/PTx/parathyroid intervention therapy and start date of procedure
- Use status of cinacalcet hydrochloride (cinacalcet hydrochloride before screening)
 - Total daily dose
 - Dosage (dosing frequency per interval)
 - Dosing period (start date of medication and end date of medication)
 - Reason of medication stopped
 - UGI tract disturbance due to cinacalcet hydrochloride
- Other items related to the inclusion and exclusion criteria

Visit [allowable window]: At the time of screening [from the time of obtaining consent until before the start of study drug administration (Week 0)]

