9.4.1.1 Hematology

Test items: WBC, WBC fraction (Baso, Eosino, Neutro, Mono, and Lymph), RBC, Ht level, Hb concentration, and PLT

Visit: [Evaluation period] Weeks 0, 2, 4, 6, 8, 10, 12, 14, 16, 18, 20, 22, and 24, and at the time of discontinuation

[Extended administration period] Weeks 8, 12, 16, 20, 24, 28, 32, 36, 40, 44, 48, and 52, at the first visit following dose increase or resumption after interruption, and at the time of discontinuation

9.4.1.2 Blood Biochemistry 1

Test items (in-hospital measurement): T-Cho, TG, TP, BUN, UA, Cr, T-Bil, AST, ALT, γ -GTP, LDH, ALP, CK, Na, K, Cl, Mg, corrected serum Ca^{*1}, Ca, Alb, and P

Visit: At the time of screening^{*2}

[Evaluation period] Weeks 0, 2, 4, 6, 8, 10, 12, 14, 16, 18, 20, 22, and 24, and at the time of discontinuation

[Extended administration period] Weeks 8, 12, 16, 20, 24, 28, 32, 36, 40, 44, 48, and 52, at the first visit following dose increase or resumption after interruption, and at the time of discontinuation

*1: If the serum Alb value is less than 4.0 g/dL, the serum Ca level will be corrected according to the following formula. If the serum Alb level is 4.0 g/dL or higher, the actual serum Ca level will be handled as the corrected serum Ca level.

Corrected serum Ca level (mg/dL) = actual serum Ca level (mg/dL) + 4 - serum Alb value (g/dL)

*2: Ca, corrected serum Ca level, and Alb will be measured. In the event that the test result does not meet inclusion criteria 4), re-testing may be performed. If performed in Week 0, it will be handled as a test result in Week 0.

9.4.1.3 Blood Biochemistry 2

Test items (central measurement): Intact PTH and whole PTH levels

Visit: [Evaluation period] Weeks 0, 2, 4, 6, 8, 10, 12, 14, 16, 18, 20, 22, and 24, and at the time of discontinuation

[Extended administration period] Weeks 8, 12, 16, 20, 24, 28, 32, 36, 40, 44, 48, and 52, at the first visit following dose increase or resumption after interruption, and at the time of discontinuation

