9.4.2 Vital Signs and Other Tests

The following tests will be performed, and the date of measurement and test results will be entered into the eCRF. The tests in Week 0 will be performed before the first administration of the study drug. The

allowable window for the timing of measurement of test items will be within 4 days before and after the scheduled visit dates during the period from Week 2 to Week 24, and within 7 days before and after the scheduled visit dates thereafter.

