9.4.4 Pregnancy Test

Test item: Pregnancy status*

Visit: At the time of screening, Week 52, and at the time of discontinuation

*: Female subjects only. However, no pregnancy test is required if at least 12 months have passed since the last menstrual period without any other medical reason.

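### No pregnancy test is planned between screening and the first dose, an interval with no stated limit, and Week 0 blood pressure need not be checked against eligibility before dosing

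*Combined protocol and SAP*

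**What the plan says.** - **Order of events.** Section 9.1 states that "the study drug will be administered to subjects whose eligibility has been confirmed and for whom registration has been completed". Section 8.2 has the investigator check every inclusion and exclusion criterion. Registration opens once those results are in hand and may take place at any time up to the first dose. Table 9.1-1 puts the registration column ahead of Week 0.
- **Pregnancy.** Exclusion 10) in 6.3 is worded around the test at screening. Section 9.4.4 schedules the test "At the time of screening, Week 52, and at the time of discontinuation". It applies to female subjects, except those whose last period was at least 12 months ago with no other medical reason. Section 4.1 defines screening as running from consent to the first dose and sets no maximum length. Contraception is instructed from consent in women of childbearing potential (10.3.3). Pregnancy is to be reported promptly and calls for measures such as immediate withdrawal (10.3.4).
- **Blood pressure.** Exclusion 7) in 6.3 reads "Uncontrolled hypertension or diabetes", with no numerical limit. Vital signs are first scheduled at Week 0 (9.4.2.3). On their timing, 9.4.2 says: "The tests in Week 0 will be performed before the first administration of the study drug".
- **Other tests.** For screening blood, Table 9.1-1 footnote b says: "Corrected serum Ca, Ca, and Alb levels will be measured". The 12-lead ECG (9.4.3) and the full biochemistry panel (9.4.1.2) start at Week 0, also before the first dose.
- **Other eligibility information.** Section 9.2 collects past history and complications before dosing, together with "Other items related to the inclusion and exclusion criteria".

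**The concern.** The protocol treats exposure in pregnancy as something to prevent, yet the only planned pre-dose test can lie an unspecified time before Day 1. A site could follow the schedule exactly and dose a woman who became pregnant after a negative screening test, or whose pregnancy was too early to detect at that test.

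The blood pressure issue is of the same kind but smaller. A planned measurement that bears directly on a listed exclusion is first taken on the day of dosing. The plan says when it is measured, but not that anyone compares it with the exclusion before the tablet is given. At stake in both cases is the safety of individual subjects whom the protocol means to keep off study drug.

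**Working it through.** No figure in the plan rests on this point, so the check sets the provisions side by side.

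| Item | Criterion it bears on | Planned before first dose | Limit on its age, or duty to review before dosing | Next planned |
|---|---|---|---|---|
| Pregnancy test | Exclusion 10) | Screening only | No limit on age | Week 52 or discontinuation |
| Blood pressure | Exclusion 7), hypertension | Week 0, pre-dose | No stated duty to review | Week 2 |
| ECG | None by a stated limit | Week 0, pre-dose | No stated duty to review | Week 2 |
| Liver tests | None by a stated limit | Week 0, pre-dose | No stated duty to review | Week 2 |

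**Pregnancy test interval.** Let s be the number of days from the screening test to Day 1.

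1. The documents put no upper bound on s. Footnote b to Table 9.1-1 lets the calcium test be repeated when inclusion 4) is not met. That can lengthen s, and no repeat pregnancy test is attached to it. Re-registration under 8.3 differs, because it requires new consent and a fresh screening.
2. After Day 1, a subject who completes the study is next tested at Week 52, which is 52 × 7 = 364 days later. With the ±7-day window in 9.1 this becomes 357 to 371 days.
3. The interval between planned tests is therefore s + 357 to s + 371 days. No visit from Week 2 to Week 48 carries a test unless the subject discontinues.

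This is the time to the next *planned test*, not to recognition of a pregnancy. Self-reporting under 10.3.4 and ordinary care would usually act sooner, but neither is tied to the first dose.

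**Blood pressure.** Registration may be completed before Week 0. Sections 9.4.2 and 9.4.3 fix when the Week 0 measurements are *performed*. Neither these sections nor 8.2 or 9.1 says that the results are *reviewed* against 6.3 before dosing. Footnote b links a Week 0 test to eligibility for calcium only.

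**What is drawn at screening.** The total in 9.6 can be reproduced from Tables 9.6-1 and 9.6-2: screening 2 mL; Week 0, 12 + 4 × 2 = 20 mL; Weeks 2 to 24, 7 × 12 + 5 × 10 = 134 mL; samples after the evaluation period, 4 × 2 = 8 mL; Weeks 28 to 52, 7 × 10 = 70 mL. The sum is 2 + 20 + 134 + 8 + 70 = 234 mL, in 1 + 5 + 12 + 4 + 7 = 29 collections. Both match the plan. The 2 mL of biochemistry 1 at screening, against 4 mL at Week 0, agrees with the short screening panel.

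**The case against.** The strongest reply is that the plan already covers most of this. Section 8.2 requires all criteria to be checked and the registration center to verify eligibility. Section 9.2 gathers history and any other criteria-related items. A positive screening pregnancy test excludes the woman before dosing, contraception starts at consent, and screening may in practice be short. All laboratory tests except PTH are run at the site (9.4.1), and blood pressure and ECG can be read at once. Registration may be as late as the first dose, so pre-dose reading is possible. The Case Registration Form, which may list the checks, is in a supplementary volume that is not part of these documents.

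Most of that stands, and it rules out several stronger readings that a reader might infer:

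- *Eligibility rests on calcium, albumin and a pregnancy test alone.* Sections 8.2 and 9.2 contradict this.
- *The pregnancy test may be of any age.* It belongs to screening and follows consent. What is missing is a maximum interval from the test to the first dose.
- *Exclusions 5) and 6) are found too late because ECG and liver tests come at Week 0.* Exclusion 5) is illustrated by functional class and exclusion 6) by antiviral treatment. Neither has an ECG or liver-test limit, so these tests are not the plan's stated means of finding them.
- *Diabetes in exclusion 7) is tested too late.* The listed tests contain no blood glucose or HbA1c, so timing is not the issue.
- *One such subject could decide the trial.* With 10 subjects, 4 responders give an exact lower limit of 12.2% and 3 give 6.7%, against the 11% threshold. That holds for the loss of any responder for any reason. The documents give no frequency for this one, so it is not evidence for the point.

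The reply leaves two things open. Contraception and self-reporting do not test for pregnancy before the first dose, and permission to read a result before dosing is not a requirement to do so.

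**Conclusion.** The point holds in a narrow form. The firmer half is pregnancy: one pre-dose test, no maximum interval from that test to Day 1, no repeat at Week 0, and 52 weeks (357 to 371 days with the window) to the next planned test in a subject who completes. The weaker half is blood pressure, which is measured before the first dose with no stated duty to check it against exclusion 7) by then. For ECG and laboratory results, the missing review sentence is a lack of detail rather than a failure to apply a stated criterion.

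The number of women affected and the usual length of screening are not given, so no frequency is estimated. The conclusion assumes that the schedule is followed as written and that the supplementary volume adds no pre-dose test or review. It is a safety wording point and does not bear on the validity of the primary analysis.

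**What to change.** 1. In Table 9.1-1 and 9.4.4, add a pregnancy test at Week 0, before the first dose, for the women already tested at screening. Exclusion 10) names only the screening test, so its wording should be aligned with the added test.
2. In 9.1, add a sentence that the Week 0 pre-dose vital signs, and any ECG and site-run laboratory results available that day, are reviewed against the existing exclusion criteria before the first dose.
3. Leave baseline corrected serum Ca at Week 0. Moving Week 0 biochemistry to an earlier day would also move the baseline for the secondary endpoint of a decrease of at least 1.0 mg/dL. No new clinical limit is needed or proposed.

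The cost is one repeat pregnancy test in a few women, a short wait on Day 1, and protocol wording. No analysis changes.
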